## 6.4 Dose-Modification Guidelines

### 6.4.1 Recommended Ixazomib Criteria for Beginning or Delaying a Subsequent Treatment Cycle & Dose Modifications for Treatment Associated Toxicity

Treatment with ixazomib will use a cycle length of 28 days. For a new cycle of treatment to begin, the patient must meet the following criteria:

- ANC must be  $\geq 1,000/\text{mm}^3$ .
- Platelet count must be  $\geq 50,000/\text{mm}^3$ .
- All other nonhematologic toxicity (except for alopecia) must have resolved to  $\leq$  Grade 1 or to the patient's baseline condition

If the patient fails to meet the above-cited criteria for initiation of the next cycle of treatment, dosing should be delayed for 1 week. At the end of that time, the patient should be re-evaluated to determine whether the criteria have been met. If the patient continues to fail to meet the above-cited criteria, delay therapy and continue to reevaluate. The maximum delay before treatment should be discontinued will be 3 weeks or at the discretion of the Principal Investigator.

For dosing recommendations upon recovery, refer to Table 6-2 and Table 6-3.

**Table 6-1 MLN908 Dose Adjustments**

Dose Level	Dose (mg)
Starting Dose	4.0 mg
-1	3.0 mg

-2	2.3 mg
-3	Discontinue

### 6.4.2 Dosage in Patients with Renal Impairment

Reduce the starting dose of Ixazomib (MLN908) to 3 mg in patients with severe renal impairment (creatinine clearance less than 30 mL/min) or end-stage renal disease (ESRD) requiring dialysis. Ixazomib is not dialyzable and therefore can be administered without regard to the timing of dialysis

**Dosage adjustments for hematologic toxicity are outlined in Table 6-2.**

**Table 6-2 Ixazomib Dose Adjustments for Hematologic Toxicities**

Criteria	Action
Within-Cycle Dose Modifications	

 
• If platelet count <math>\leq 30 \times 10^9/L</math> or ANC <math>\leq 0.50 \times 10^9/L</math> on a ixazomib dosing day (other than Day 1)
 
	
 
• Ixazomib dose should be withheld.
 
• Complete blood count (CBC) with differential should be repeated at least every other day until the ANC and/or platelet counts have exceeded the prespecified values (see Section 6.3.1) on at least 2 occasions.
 
• Upon recovery, ixazomib may be reinitiated with 1 dose level reduction.
 

Dose Modifications for Subsequent Treatment Cycles	

 
• Delay of > 2 weeks in the start of a subsequent cycle due to lack of toxicity recovery as defined in Section 6.3.1.
 
• ANC <math>< 1.0 \times 10^9/L</math>, platelet count <math>< 50 \times 10^9/L</math>
 
	
 
• Hold ixazomib until resolution as per criteria Section 6.3.1.
 
• Upon recovery, reduce ixazomib 1 dose level.
 
• The maximum delay before treatment should be discontinued will be 3 weeks or at the discretion of the PI.
 

Dose Modifications for Subsequent Treatment Cycles	

 
• All hematologic toxicities
 
	
 
• For hematologic toxicity that occurs during a cycle but recover in time for the start of the next cycle,:                             
 
○ If dose was reduced within the cycle, start the next cycle at that same dose.
 
○ If due to toxicity timing, i.e., after Day 15 dosing thus a dose reduction was not required at that point in the cycle, reduce ixazomib by 1 dose level at the start of that cycle.
 
○ Do not reduce the dose both within a cycle and at the start of the cycle for the same most severe toxicity.
 
 
 

Treatment modifications due to ixazomib-related AEs are outlined in Table 6-3.

**Table 6-3 Ixazomib Treatment Modification (Delays, Reductions, and Discontinuations) Due to Adverse Events (Non-Hematologic Toxicities)**

Adverse Event (Severity)	Action on Study Drug	Further Considerations
Peripheral Neuropathy:		
Grade 1 peripheral neuropathy	
 
No action
 
	Grade 1 signs and symptoms: asymptomatic; without pain or loss of function; clinical or diagnostic observations only [14]
New or worsening Grade 1 peripheral neuropathy with pain or Grade 2	
 
Hold study drug until resolution to Grade <math>\leq</math> 1 or baseline
 
	Grade 2 signs and symptoms: Moderate symptoms; limiting instrumental activities of daily living (ADL) [14]
New or worsening Grade 2 peripheral neuropathy with pain or Grade 3	
 
Hold study drug until resolution to Grade <math>\leq</math> 1 or baseline
 
Reduce study drug to next lower dose upon recovery
 
	Grade 3 signs and symptoms: severe symptoms; limiting self-care ADL; assistive device indicated [14]
New or worsening Grade 4 peripheral neuropathy	
 
Discontinue study drug
 
	
Grade 2 Rash	
 
Symptomatic recommendations as per section 6.7
 
	The investigator and project clinician may discuss considerations for dose modifications and symptom management.
Grade 3 nonhematologic toxicity judged to be related to study drug	
 
Hold study drug until resolution to Grade <math><</math> 1 or baseline
 
	Symptomatic recommendations noted in Section 6.7

**Table 6-3 Ixazomib Treatment Modification (Delays, Reductions, and Discontinuations) Due to Adverse Events (Non-Hematologic Toxicities)**

Adverse Event (Severity)	Action on Study Drug	Further Considerations
If not recovered to < Grade 1 or baseline within 4 weeks	
 
Reduce study drug 1 to next lower dose upon return to < Grade 1 or baseline
 
	
Subsequent recurrence Grade 3 that does not recover to < Grade 1 or baseline within 4 weeks	
 
Hold study drug until resolution to Grade < 1 or baseline
 
Reduce study drug to next lower dose
 
	Monitor closely, take appropriate medical precautions, and provide appropriate symptomatic care
Grade 4 nonhematologic toxicities judged to be related to study drug	
 
Consider permanently discontinuing study drug
 
	Exceptions are cases in which the investigator determines the patient is obtaining a clinical benefit

Once ixazomib is reduced for any toxicity, the dose may not be re-escalated.

Rituximab and Ixazomib individually are FDA approved for NHL and multiple myeloma, respectively. The combination of a proteasome inhibitor plus anti-CD20 antibody has been studied previously.

Mechanistically, rituximab and Ixazomib does not have overlapping mechanism of action. We have in place Hepatitis screening at baseline. Rituximab does not have overlapping non-hematologic toxicity with Ixazomib. However, they will both cause cytotoxicity to hematopoietic cells, cytopenias and related increased risk for infection. We are mainly concerned for non-hematologic toxicities. Therefore, we would like to monitor peripheral neuropathy toxicities. We will stop the current dose level and consider treating patients at a lower dose level for Ixazomib if we observe at anytime that the rate of any grade of peripheral neuropathy toxicity is > 40% or the rate of grade 3 or higher peripheral neuropathy toxicity is >10%.

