#### Ixazomib Administration

All protocol-specific criteria for administration of study drug must be met and documented before drug administration. Study drug will be administered or dispensed only to eligible patients under the supervision of the investigator or identified subinvestigator(s). Patients should be monitored for toxicity, as necessary, and doses of ixazomib should be modified as

needed to accommodate patient tolerance to treatment; this may include symptomatic treatment, dose interruptions, and adjustments of ixazomib dose (see Section 6.3).

Capsules of ixazomib will also be referred to as study drug. Study drug will be supplied by Millennium as capsules of 2.3-, 3.0- and 4.0 mg ixazomib.

The prescribed administration of ixazomib doses in this study is 4 mg ixazomib in a 28 day cycle.

Patients should be instructed to swallow ixazomib capsules whole, with water, and not to break, chew, or open the capsules. Ixazomib should be taken on an empty stomach (no food or drink) at least 1 hour before or at least 2 hours after food. Each capsule should be swallowed separately with a sip of water. A total of approximately 8 ounces (240 mL) of water should be taken with the capsules.

Missed doses can be taken as soon as the patient remembers if the next scheduled dose is 72 hours or more away. A double dose should not be taken to make up for a missed dose. If the patient vomits after taking a dose, the patient should not repeat the dose but should resume dosing at the time of the next scheduled dose.

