### **Thrombocytopenia**

Blood counts should be monitored regularly as outlined in the protocol with additional testing obtained according to standard clinical practice. Thrombocytopenia may be severe but has been manageable with platelet transfusions according to standard clinical practice. Ixazomib administration should be modified as noted as per dose modification recommendations in the protocol when thrombocytopenia occurs (see Table 6-2). Therapy can be reinitiated at a reduced level upon recovery of platelet counts. A rare risk is thrombotic thrombocytopenic purpura (TTP), a rare blood disorder where blood clots form in small blood vessels throughout the body

characterized by thrombocytopenia, petechiae, fever, or possibly more serious signs and symptoms. TTP should be managed symptomatically according to standard medical practice.

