## **6.10 Storage, Handling, and Accountability**

Upon receipt at the investigative site, ixazomib should remain in the blister and carton provided until use or until drug is dispensed. The container should be stored at the investigative site as per

labeled instructions (do not store above 30°C or 86°F, do not freeze). Ensure that the drug is used before the retest expiry date provided by Millennium. Expiry extensions will be communicated accordingly with updated documentation to support the extended shelf life.

In countries where local regulations permit, ixazomib capsules dispensed to the patient for take-home dosing should remain in the blister packaging and stored per labeled instructions as noted above until the point of use. The investigative site is responsible for providing the medication to the patient in the correct daily dose configurations. Comprehensive instructions should be provided to the patient in order to ensure compliance with dosing procedures. Patients who are receiving take-home medication should be given only 1 cycle of medication at a time. Patients should be instructed to store the medication per labeled instructions (not store above 30°C or 86°F, do not freeze) for the duration of each cycle. Patients should be instructed to return their empty blister packs to the investigative site, rather than discarding them. Reconciliation will occur accordingly when the patient returns for their next cycle of take-home medication. Any extreme in temperature should be reported as an excursion and should be dealt with on a case-by-case basis.

Ixazomib should be handled with due care. Patients should be instructed not to chew, break, or open capsules. In case of contact with broken capsules, raising dust should be avoided during the clean-up operation. The product may be harmful by inhalation, ingestion, or skin absorption. Gloves and protective clothing should be worn during cleanup and return of broken capsules and powder to minimize skin contact.

The area should be ventilated and the site washed with soap and water after material pick-up is complete. The material should be disposed of as hazardous medical waste in compliance with federal, state, and local regulations.

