**11.3 SCHEDULE OF STUDY ASSESSMENTS**

Days (+/-3d)	Screening A	C1D1	C2D1	C3D1	C4D1	C5D1	C6D1	C7D1	C8D1	C9D1	C10D1	C11D1	C12D1	C13D1	C14D1	C15D1+	EOS (+/- 7 days)
Informed consent, review inclusion/exclusion, general medical history B	X																
Vital signs, weight and height	X	X	X	X	X	X	X	X	X	X	X	X	X	X	X	X	X
ECOG and B symptoms C	X	X	X	X	X	X	X	X	X	X	X	X	X	X	X	X	X
Physical Exam D	X	X	X	X	X	X	X	X	X	X	X	X	X	X	X	X	X
12 lead ECG and ECHO E	X																
PET/CT or CT scan F	X				X F				X F				X F			X F	X F
Bone marrow biopsy/aspirate G	X				X G				X G							X G	X
MRD assessment H	X				X H				X H							X H	X
Tumor biopsy	X																X
CBC, CMP, and Hepatitis Testing i,j	X	X	X	X	X	X	X	X	X	X	X	X	X	X	X	X	X J

Days (+/-3d)	Screening A	C1D1	C2D1	C3D1	C4D1	C5D1	C6D1	C7D1	C8D1	C9D1	C10D1	C11D1	C12D1	C13D1	C14D1	C15D1	
Quantitative Immunoglobulins	X																
Pregnancy Test	X																

Footnotes Table of Assessments

- A. Perform within 28 days prior to cycle 1 day 1. Assessments performed as standard of care may be used for screening. *BIOPSY TISSUES* obtained up to 8 weeks prior to start of C1D1 can be used as long as we have enough tissue for analysis.
- B. Written informed consent form(s) must be signed by the patient before any study specific procedures are performed.
- C. B symptoms: Unexplained weight loss>10% over previous 6 months, fever (>38C) and/or drenching night sweats.
- D. Complete physical exam at screening, including cardiovascular, respiratory, abdominal, lymph node, skin ENT, extremities and endocrinological examination. Targeted physical exams at subsequent visits, limited to systems of clinical relevance, (i.e., cardiovascular, respiratory, lymph nodes, liver, and spleen), and dose systems associated with clinical signs/symptoms.
- E. Single 12-lead ECG and Echo is required at screening. If clinically significant abnormality is noted by the attending physician, a referral to cardiology will be made.

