**Special Attention**

Patients who wish to continue with ixazomib after completion of week 56 can continue on with therapy with ixazomib single agent. Rituximab will not be continued post week 56.

End of study biopsy and MRD testing is required.

Medications	C1D1	C1D8	C1D15	C1D21	C2 and Beyond
Rituximab	X	X	X	X	Rituxan to continue C3D1, with each cycle D1
Ixazomib	X	X	X		Continue days 1, 8 and 15 of each cycle.
TLS Assessment A	X	X	X	X	Continue days 1, 8 and 15 of each cycle.
Physical Exam	X				
CBC	X	X	X	X	
CMP	X	X	X	X	

- A. Patients should be assessed for risk and should receive appropriate prophylaxis for TLS, including hydration and anti-hyperuricemics. Monitor blood chemistries and manage abnormalities promptly. Interrupt dosing if needed. Employ more intensive measures (intravenous hydration, frequent monitoring, hospitalization) as overall risk increases

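### From Cycle 2, no blood count is scheduled on Day 8 or Day 15, the days on which Table 6-2 requires ixazomib to be withheld for low counts

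*Combined protocol and SAP*

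**What the plan says.** **Dosing rule.** Section 6.2 gives ixazomib on Days 1, 8 and 15 of each 28-day cycle. The within-cycle part of Table 6-2 withholds the dose if platelets are at or below 30 x 10^9/L or ANC is at or below 0.50 x 10^9/L "on a ixazomib dosing day (other than Day 1"). It is not limited to Cycle 1. A second rule in the table covers hematologic toxicity that recovers before the next cycle: "If due to toxicity timing, i.e., after Day 15 dosing thus a dose reduction was not required at that point in the cycle", the next cycle starts one dose level lower. Section 6.2, Ixazomib Administration, adds a general duty: "All protocol-specific criteria for administration of study drug must be met and documented before drug administration".

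**Schedule.** In the main table of Section 11.3, the row "CBC, CMP, and Hepatitis Testing" is marked at screening, on Day 1 of each cycle and at end of study. That table has no Day 8 or Day 15 column. The dosing table under Special Attention marks CBC on C1D1, C1D8, C1D15 and C1D21 and shows nothing for it under *C2 and Beyond*. In that same column, ixazomib and the TLS assessment both read "Continue days 1, 8 and 15 of each cycle".

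**Dispensing and general monitoring.** Section 6.10 says "Patients who are receiving take-home medication should be given only 1 cycle of medication at a time" and "Reconciliation will occur accordingly when the patient returns for their next cycle of take-home medication". Section 6.7, Thrombocytopenia, says "Blood counts should be monitored regularly as outlined in the protocol with additional testing obtained according to standard clinical practice"; the neutropenia paragraph gives the same instruction.

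**The concern.** The within-cycle hold can act only on a count from the day of dosing. From Cycle 2 the plan gives the dose on Days 8 and 15 but schedules no count on either day. A site that follows the schedule exactly would have nothing to compare with the limits in Table 6-2. A patient may also already hold the capsules for the whole cycle at home.

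What is at stake is whether a stated safety rule works as written. Section 6.4 acknowledges that both drugs cause cytopenias and a related infection risk. Section 6.4.1 lets a cycle start at platelets of 50,000/mm³ and ANC of 1,000/mm³, not far above the hold limits. There is also a smaller reporting issue. Section 7.1.6 tabulates the maximum grade of each toxicity, and a mid-cycle low count that nobody measured cannot appear there.

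**Working it through.** The plan gives no figure on this point to reproduce. The check sets the dosing rule beside the schedule and then counts doses.

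**Step 1. When the hold applies.** Doses fall on Days 1, 8 and 15. Excluding Day 1 leaves Days 8 and 15 of every cycle.

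**Step 2. Which of those days have a scheduled CBC.**

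| Source | Cycle 1 | Cycle 2 onward |
|---|---|---|
| 11.3, main schedule | Day 1 | Day 1 |
| 11.3, Special Attention table | Days 1, 8, 15, 21 | none shown |
| Both combined | Days 1, 8, 15, 21 (4 counts) | Day 1 (1 count) |

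**Step 3. Whether other scheduled blood work supplies the count.** The TLS assessment continues on Days 1, 8 and 15, and Sections 6.3.2 and 6.3.3 ask for pre-dose chemistries. Footnote I of 11.3 lists the panel: electrolytes, renal and liver markers, LDH, uric acid and similar. It contains neither platelets nor ANC. Table 6-2 does require repeat counts at least every other day, but only once a hold has begun, so it does not provide the first count.

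**Step 4. Count of doses, Cycles 1 to 12.**
- Non-Day-1 doses: 2 x 12 = 24.
- With a scheduled same-day CBC: C1D8 and C1D15 = 2.
- Without: 24 − 2 = 22, and 22/24 = 91.7%.
- Of all ixazomib doses: 3 x 12 = 36. With a same-day CBC: 3 in Cycle 1 + 11 on Day 1 of Cycles 2 to 12 = 14. Without: 36 − 14 = 22, and 22/36 = 61%.
- Through week 56 (56/4 = 14 cycles): 2 x 14 = 28 non-Day-1 doses, 28 − 2 = 26 without a scheduled count, and 26/28 = 93%.

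**Step 5. The rule for toxicity after Day 15 dosing.** Cycle 1 has a Day 21 count. In later cycles the next scheduled count is Day 1 of the following cycle, 28 − 15 + 1 = 14 days after the Day 15 dose. The rule concerns toxicity that has recovered by then, so the Day 1 count cannot be relied on to reveal it.

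**Step 6. With the fix.** A CBC on Days 8 and 15 of every cycle raises coverage of non-Day-1 doses from 2 of 24 to 24 of 24.

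**The case against.** The best defence is that the text already requires the check. Section 6.2 wants dosing criteria met and documented before each administration, Table 6-2 makes the dosing-day count such a criterion, and a count that was not taken cannot be documented. On this reading the schedule is merely out of step with binding text, at a single center that would test by standard practice anyway. Part of this stands: the safeguard exists in the dosing rules and unscheduled counts are allowed. But the sentence in 6.2 names no test and no day, and Section 6.7 refers back to the protocol's own schedule and leaves the rest to practice. If 6.2 does imply a count before every dose, the schedule contradicts it, and that is the defect.

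A second objection is that the empty *C2 and Beyond* cell proves little. The same column is also empty for CMP and physical exam, which the main schedule does place on every Day 1, and an empty cell in a converted table cannot be fully verified. That is fair as to intent. The point does not rest on that cell alone, because the main schedule has no Day 8 or Day 15 column in any cycle.

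Three stronger readings are tempting but are not supported:
- A reader might infer that platelet transfusion near a dosing day is barred, which would make the gap more dangerous. The restriction covers transfusions given to help meet eligibility criteria; Section 6.5 allows those that are clinically indicated.
- A reader might infer a number of missed holds. The documents give no rate of counts at the hold limit, no expected number of cycles and no frequency of unscheduled counts. Early closure under Section 7.1.9 and dose reductions that may not be reversed would both lower the number.
- A reader might infer from the 2-fold accumulation in Section 1.4 that counts are lowest after Day 15. That figure describes drug exposure; no timing of the low point is given.

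**Conclusion.** The concern holds as an inconsistency between a dosing rule and the visit schedule. From Cycle 2 the within-cycle hold has no scheduled count behind it: 22 of 24 non-Day-1 doses in Cycles 1 to 12 are uncovered. The post-Day-15 reduction rule has the same weakness. This rests on reading the two tables in Section 11.3 as they stand, and it concerns scheduled counts only. How often a hold would actually be missed cannot be estimated from the documents.

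The reporting effect is secondary. Scheduled counts fall from four in Cycle 1 to one in each later cycle, so maximum platelet and neutrophil grades after Cycle 1 may be understated. A reader might extend this to later-cycle toxicity in general. That goes too far: non-hematologic grades do not depend on the CBC, and unscheduled counts can still enter the record. The primary complete-response analysis and the neuropathy monitoring rule in Section 7.1.8 are unaffected. The point merits a small amendment because the remedy is simple and lets a stated safety rule work as written.

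**What to change.** 1. In the Special Attention table of Section 11.3, give the CBC row the same *C2 and Beyond* entry as the ixazomib row, that is, Days 1, 8 and 15 of each cycle, drawn with the TLS chemistries already listed for those days.
2. In Section 6.2, add that the Day 8 and Day 15 ixazomib doses, including take-home capsules, are not taken until that day's platelet count and ANC have been reviewed against Table 6-2.
3. These changes add no count after Day 15. State in Table 6-2 that, from Cycle 2, the rule for toxicity after Day 15 dosing acts on counts taken for clinical reasons.

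If fewer counts are intended in later cycles, the protocol should instead name the last cycle with Day 8 and Day 15 counts and say that the within-cycle hold then applies only to counts taken for clinical reasons.

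**Cost.** Two extra CBCs per cycle from Cycle 2, so 2 x 11 = 22 per patient over Cycles 2 to 12 and at most 24 x 22 = 528 for the study if every patient completes 12 cycles. No new visit is needed where the Day 8 and Day 15 chemistries are drawn as listed. Each of those doses waits for a result, and more holds may follow.

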## 5.2 Exclusion Criteria

Patients meeting any of the following exclusion criteria are not to be enrolled in the study:

1. Female patients who are lactating or have a positive serum pregnancy test during the screening period.
2. Failure to have fully recovered (i.e.,  $\leq$  Grade 1 toxicity) from the reversible effects of prior chemotherapy.
3. Major surgery within 14 days before enrollment.

4. Radiotherapy within 14 days before enrollment. If the involved field is small, 7 days will be considered a sufficient interval between treatment and administration of the ixazomib.
5. Central nervous system involvement.
6. Infection requiring systemic antibiotic therapy or other serious infection within 14 days before study enrollment. Patient may be eligible, if infectious disease specialist approves start of therapy AND subject has completed course of antibiotic therapy.
7. Evidence of current uncontrolled cardiovascular conditions, including uncontrolled hypertension, uncontrolled cardiac arrhythmias, symptomatic congestive heart failure, unstable angina, or myocardial infarction within the past 6 months.
8. Systemic treatment, within 14 days before the first dose of ixazomib, with strong CYP3A inducers (rifampin, rifapentine, rifabutin, carbamazepine, phenytoin, phenobarbital), or use of St. John's wort.
9. Ongoing or active systemic infection, active (DNA PCR positivity) hepatitis B or C virus infection, or known human immunodeficiency virus (HIV) positive.
10. Any serious medical or psychiatric illness that could, in the investigator's opinion, potentially interfere with the completion of treatment according to this protocol.
11. Known allergy to any of the study medications, their analogues, or excipients in the various formulations of any agent.
12. Known GI disease or GI procedure that could interfere with the oral absorption or tolerance of ixazomib including difficulty swallowing.
13. Diagnosed or treated for another malignancy within 2 years before study enrollment or previously diagnosed with another malignancy and have any evidence of residual disease. Patients with nonmelanoma skin cancer or carcinoma in situ of any type are not excluded if they have undergone complete resection.
14. Patient has  $\geq$  Grade 3 peripheral neuropathy, or Grade 2 with pain on clinical examination during the screening period.

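### Table 6-3: the hold for painful Grade 1 neuropathy is either already released when it starts or has a trigger that the table's own Grade 1 description rules out

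*Combined protocol and SAP*

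**What the plan says.** The peripheral neuropathy part of Table 6-3 has four graded rows.

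- Grade 1: no action. The accompanying note reads "Grade 1 signs and symptoms: asymptomatic; without pain or loss of function; clinical or diagnostic observations only".
- "New or worsening Grade 1 peripheral neuropathy with pain or Grade 2": the action is "Hold study drug until resolution to Grade" 1 or lower, or baseline. No dose reduction is attached. The note describes Grade 2 as moderate symptoms that limit instrumental daily activities.
- "New or worsening Grade 2 peripheral neuropathy with pain or Grade 3": the same hold and the same release condition, plus a reduction to the next lower dose on recovery.
- Grade 4: discontinue.

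No release condition mentions pain. Pain does appear as a qualifier on grade at eligibility: exclusion criterion 14 in Section 5.2 bars Grade 3 or higher neuropathy, or "Grade 2 with pain on clinical examination during the screening period". The text after Table 6-3 gives neuropathy special standing: "Therefore, we would like to monitor peripheral neuropathy toxicities".

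**The concern.** The authors separated painful Grade 1 neuropathy from ordinary Grade 1 and gave it a hold. The release level written for that hold is the same grade that triggers it, and the neighboring note says that Grade 1 has no pain. The one entry that distinguishes painful from painless Grade 1 may therefore do nothing, or may describe no one.

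What is at stake is the rule for the individual patient, in the toxicity that the protocol singles out for monitoring. Ixazomib is given on Days 1, 8 and 15 (Section 6.2). If a hold ends as it begins, the next dose falls due on schedule. Two investigators reading the same table could then treat similar patients differently.

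**Working it through.** No sample size, error rate or estimate is involved, so there is no figure to reproduce. The check compares each trigger with its release condition, which is Grade 1 or lower OR baseline. Because the two parts are joined by or, meeting either one is enough.

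**Reading A: grade taken as a number, pain as an added qualifier**

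| Trigger | Grade at trigger | Is grade ≤ 1 at onset? | Result |
|---|---|---|---|
| Grade 1 with pain | 1 | Yes, 1 ≤ 1 | Hold released at onset |
| Grade 2, same row | 2 | No, 2 > 1 | Hold works |
| Grade 2 with pain, next row | 2 | No, 2 > 1 | Hold works |
| Grade 3, next row | 3 | No, 3 > 1 | Hold works |

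The baseline part does not rescue the first line, because the grade part is already satisfied. The row carries no dose reduction, so for painful Grade 1 it has the same effect as the row above it, which takes no action.

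**Reading B: Grade 1 taken as the table's note describes it**

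Resolution to Grade 1 now requires the pain to have gone, so the release condition has content. By the same description, however, a patient with pain is not Grade 1, so the trigger of Grade 1 with pain cannot occur. Nor does mild pain that leaves instrumental activities intact fit the Grade 2 note. Such a patient matches neither description.

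**Does another section close the gap?**

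- Section 6.4.1, on starting a new cycle, says "All other nonhematologic toxicity (except for alopecia) must have resolved to" Grade 1 or lower, or the patient's baseline. The threshold is the same and pain is again not mentioned.
- Section 6.5 allows patients with worsening neuropathy to be observed, with delays or reductions as the protocol indicates. It points back to Table 6-3.
- Section 6.7, on managing clinical events, has no peripheral neuropathy entry.
- The grade notes cite reference 14. In Section 10 that is a phase 1 dose-escalation abstract in multiple myeloma; the CTCAE is reference 17. The citation does not lead to the grading criteria.

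**Reach into the analyses**

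- The rule after Table 6-3 uses neuropathy of any grade (above 40%) and Grade 3 or higher (above 10%). Recording an event as Grade 1 or Grade 2 changes neither count.
- The Bayesian boundary in Section 7.1.8 uses Grade 3 or higher only. It is unchanged.
- Section 7.1.6 tabulates the maximum grade of each toxicity. Here a Grade 1 versus Grade 2 decision could move a patient between two cells.

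**The case against.** The best defense is that any clinician would hold until the pain resolves. The word resolution implies a change of state, and exclusion criterion 14 shows that the protocol uses pain as a qualifier on a numeric grade. This is probably what the authors meant. The table does not say it, though: the reading needs Grade 1 to allow pain in the trigger and to exclude it in the release, within one row.

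A second defense is that painful Grade 1 is named in its own row, so an investigator should not fall back on the general no-action row. That is fair. The named row is the natural choice, but its hold is still met at onset when grade is read as a number.

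A third is discretion. Section 6.2 lets doses be interrupted or adjusted for tolerance, and Section 6.5 allows observation and supportive care. This stands as a limit on the consequences: the documents do not oblige anyone to keep dosing through painful neuropathy. It does not repair the rule.

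Three stronger readings are tempting but not supported.

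- A reader might infer that the next row has the same fault. It does not. Grade 2 with pain and Grade 3 both lie above the release level, and that row also reduces the dose. Its release condition ignores pain, but residual Grade 1 after improvement is not clearly new or worsening, so restarting in that state does not plainly contradict the row above.
- A reader might infer variation between sites. Section 4.1 describes a single-center study, so any variation is between investigators.
- A reader might infer that the neuropathy stopping rules are compromised. They do not depend on the split between Grade 1 and Grade 2.

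**Conclusion.** The painful Grade 1 limb of one row in Table 6-3 is wrong as written. Read numerically, its hold has no duration; read by the table's own description, its trigger is empty. No single meaning of Grade 1 makes the limb work. The defect is confined to that limb.

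Its size cannot be given as a rate, because the documents give no expected frequency of painful Grade 1 neuropathy. The consequence is inconsistent individual dosing decisions and, at most, some movement between Grade 1 and Grade 2 in a descriptive table. No efficacy estimate, sample-size figure or stopping boundary changes. The point still merits correction, because it is a stated safety rule in the toxicity chosen for monitoring.

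The conclusion rests on reading the release condition literally, with either part sufficient. The results for Grade 2 and above assume a patient who entered at Grade 1 or lower; exclusion criterion 14 also admits painless Grade 2, for whom release depends on how baseline is understood.

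**What to change.** Reconcile three entries in Table 6-3: the Grade 1 description, the pain trigger in the following row, and that row's release condition. After the change, a patient with painful low-grade neuropathy should fall in exactly one row, and the hold should not already be satisfied when it is triggered. While the cells are open, the sponsor could also state whether pain bears on release for the Grade 2 limb and the next row, where the text is silent but not contradictory. What the rule should be is for the sponsor's clinicians to decide; this review proposes none.

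The cost is a wording change to a few table cells, with no added procedures. Depending on the content chosen, some holds may last longer.
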